7.3 LOST TO FOLLOW-UP

A participant will be considered lost to follow-up if he or she fails to return for a scheduled visit and is unable to be contacted by the study site staff.

The following actions must be taken if a participant fails to return to the clinic for a required study visit:

- The site will attempt to contact the participant and reschedule the missed visit within 2 weeks and counsel the participant on the importance of maintaining the assigned visit schedule and ascertain if the participant wishes to and/or should continue in the study.
- Before a participant is deemed lost to follow-up, the investigator or designee will make every effort to regain contact with the participant (where possible, 3 telephone calls and, if necessary, a certified letter to the participant's last known mailing address or local equivalent methods). These contact attempts should be documented in the participant's medical record or study file.
- Should the participant continue to be unreachable, he or she will be considered to have withdrawn from the study with a primary reason of lost to follow-up.

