1 PROTOCOL SUMMARY

1.1 SYNOPSIS

Title:	Pilot Study of Omega-3 Polyunsaturated Fatty Acid Treatment in Mild Acute TBI (OPTIMA-TBI pilot).
Study Description:	This is a double-blinded randomized control trials comparing the effect of omega-3 fatty acid versus placebo on blood biomarkers of brain injury, inflammation and neurogenesis.
Objectives:	
Primary Objective: Biomarker endpoints include: neuronal injury measured by Neurofilament light chain (NFL), Neurogranin (NRGN) and Intercellular adhesion molecule 5 [ICAM5]; inflammation measured by high sensitivity C-reactive protein (CRP), IL-6 and IL-10 and neurogenesis measured by brain derived neurotrophic factor (BDNF)
 
Secondary Objectives:
 
1. Delayed functional recovery defined as Glasgow Outcome Scale Extended (GOSE)<8 at 3 months2. Moderate/severe post-concussive symptoms at 3 months defined as having at least three symptoms in at least three following ICD-10 symptom categories obtained from the Rivermead Post-Concussion Questionnaire (RPQ): (1) headaches, dizziness, general malaise, excessive fatigue, or noise intolerance; (2) irritability, emotional lability, depression, or anxiety; (3) subjective complaints of concentration or memory difficulty; (4) insomnia; (5) reduced tolerance to alcohol; (6) preoccupation with these symptoms and fear of permanent brain damage.3. Cognitive impairment at 3 months is defined based on a battery of 13 neurocognitive tests. Subjects are deemed cognitively impaired if their scores on at least 2 neurocognitive tests are more than 2 standard deviations below their IQ T-Score ascertained by the Wechsler Test of Adult Reading (WTAR).4. Serious adverse events (SAEs): Life-threatening bleed including upper GI bleed, intracranial hemorrhage; hypotension; severe allergic reaction, blood glucose and LDL cholesterol levels
Endpoints:	
Primary Endpoint: Serum levels of neurofilament light chain, C-reactive protein, IL-6, IL-10, Brain derived neurotrophic factor over a 3-month period
 
Secondary Endpoints: Functional recovery (measured by Glasgow Coma Scale Extended), symptomatic recovery (measured by the Rivermead Post-concussive Symptoms Questionnaire) and cognitive impairment (measured by a cognitive battery) at 3 months post injury

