5.4 STRATEGIES FOR RECRUITMENT AND RETENTION

Potential subject for this trial will be recruited from all patients with mild TBI (GCS 13-15) presenting within 7 days of injury to the University of Michigan Emergency Department. Trained research personnel will perform enrollment of subjects.

Target sample size: 50 participants

Anticipated accrual rate: 5-10 patients per month

Anticipated number of sites: 1

Source of participants: Emergency Department and Inpatient admissions of the University Hospital, University of Michigan

How potential participants will be identified and approached: Trained research coordinators will screen the Emergency Department Dashboard of MiChart for eligible patients. They will then approach emergency physicians/physician assistants taking care of eligible patients and ask for permission to approach their patient to further discuss the study and obtain informed consent. This will occur in the emergency department. If the potential subject agrees to the referral, the research coordinator will approach the potential subject and begin the consent process. This process will help maintain patient privacy, by allowing potential subjects to have control over who has access to them. For patients lacking the capacity to consent, an authorized legal representative will be identified for consent purposes. Participation in the study will be voluntary.

Incentives for visit attendance: A cash incentive of \$75 will be provided for attending the 2 week visit, \$75 for attending the 1 month visit and \$150 for attending the 3 month visit.

Inclusion of women and minorities: Traumatic brain injury occurs more frequently in men. However, efforts will be made to ensure that all eligible women are included. Additionally, efforts will be made to ensure an adequate representation of under-represented minorities.

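### Sections 7.3 and 7.2 class a participant who is unreachable at an early visit as withdrawn and have them replaced, with no provision for seeking the 3-month outcome or for return

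*Combined protocol and SAP*

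**What the plan says.** Section 7.3 sets the trigger: "A participant will be considered lost to follow-up if he or she fails to return for a scheduled visit and is unable to be contacted". It names no particular visit, so each of the three follow-up visits (2 weeks, 1 month, 3 months) can start the process.

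The site then has two duties. The first is rescheduling: "The site will attempt to contact the participant and reschedule the missed visit within 2 weeks". The second is a wider search: "Before a participant is deemed lost to follow-up, the investigator or designee will make every effort to regain contact with the participant". The search means three telephone calls where possible and a certified letter if one is needed. If contact still fails, "he or she will be considered to have withdrawn from the study with a primary reason of lost to follow-up".

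Section 7.2 makes replacement mandatory for anyone who was randomised and treated and who then withdraws or is withdrawn. For those randomised but never treated, replacement is optional. The same section lists, among the reasons for which an investigator may end study participation, an interruption of study medication of two weeks or longer. Section 7.1, by contrast, keeps a participant who only stops medication in follow-up.

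The endpoints depend on the last visit. The synopsis gives the first secondary objective as "Delayed functional recovery defined as Glasgow Outcome Scale Extended (GOSE)<8 at 3 months", and places post-concussive symptoms and cognitive impairment at the same time point. The primary hypothesis in section 9.1 concerns the area under the concentration curve over the 3 months after injury.

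**The concern.** Being out of contact at 2 weeks or 1 month does not by itself mean that a person has left the trial. An early absence needs to cost only the data of that visit. Under the two rules taken together, it can also cost the 3-month visit, for someone who has not withdrawn consent.

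Three things are at stake in a trial of 50:

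- **Endpoint data.** Section 9.4.1 compares biomarkers at baseline and at 3 months. A missing interim sample leaves that contrast intact; a missing 3-month sample removes the participant from it.
- **Selection.** After mild TBI, a person may be hard to reach because of full recovery and return to work, or because of continuing symptoms. In either case reachability may be related to outcome. A replacement restores the head count but does not undo that selection, and the person replaced was the one randomised.
- **The feasibility aim.** Section 3 lists the feasibility of follow-up assessments as a secondary objective. Counting a missed interim visit as a withdrawal blurs the retention figure that the pilot is meant to supply.

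**Working it through.** The document gives no dropout or retention rate, and section 9.2 states the sample size of 50 without inputs. There is therefore no figure of the plan to reproduce. The check is mainly a reading of the rules in sequence, followed by an illustration of size.

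**Reading the rules in order, for a treated participant who cannot be reached at 2 weeks**

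1. The missed visit is one of the scheduled visits, so section 7.3 applies.
2. Rescheduling, calls and, if necessary, a letter are attempted and fail.
3. Section 7.3 classes the person as withdrawn. The wording is mandatory, whereas the investigator's own grounds for withdrawal in section 7.2 are permissive.
4. Section 7.2 requires a replacement.
5. The 3-month visit falls due. No section tells staff to try again, says whether the person may return, or says which of the two participants is analysed. Section 9.4.1 names no analysis set and no method for missing data.

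**Illustration A: outcomes that could be recovered**

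Assumed, not in the documents: 10% to 30% of 50 (5 to 15) unreachable around an early visit, and 30% to 50% of those obtainable at 3 months if sought.

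- Low end: 5 × 0.30 = 1.5, and 1.5/50 = 3%.
- High end: 15 × 0.50 = 7.5, and 7.5/50 = 15%.

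That is about 2 to 8 outcomes.

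**Illustration B: effect on precision**

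Assumed: a chance q of becoming unreachable at each of the two early visits, and a share r of those people reached at 3 months if sought. Also assumed: 1:1 allocation, two-sided 5% level, 80% power, and no other losses.

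- Classed as withdrawn before 3 months: 50 × (1 − (1 − q)²). For q = 10% this is 50 × (1 − 0.81) = 9.5.
- Detectable difference in SD units: (1.96 + 0.84) × √(4/N). For N = 50 this is 0.79.

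| q | Classed as withdrawn | N at 3 months if not sought | N if sought, r = 25% to 50% | Detectable difference, not sought | Detectable difference, sought |
|---|---|---|---|---|---|
| 5% | 4.9 | 45.1 | 46.3 to 47.6 | 0.83 | 0.82 to 0.81 |
| 10% | 9.5 | 40.5 | 42.9 to 45.2 | 0.88 | 0.86 to 0.83 |
| 15% | 13.9 | 36.1 | 39.6 to 43.1 | 0.93 | 0.89 to 0.85 |

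These counts are before any replacement under section 7.2. The gain in precision from seeking these people is modest.

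**Incentive**

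Section 5.4 pays $75 for each of the first two visits and, in dollars, "150 for attending the 3 month visit". The last visit carries 150/(75 + 75 + 150) = 50% of the total. This shows the weight the plan gives to the 3-month visit; it says nothing about contact attempts.

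**The case against.** The strongest reply is that section 7.3 does not say what a hurried reader may take from it. Such a reader might infer that withdrawn status is permanent, that the site stops looking, or that classification happens at about week 4. None of this is written. The two-week period belongs to rescheduling the missed visit and is not a deadline for classification. The condition of remaining unreachable has no end date and could be read as applying only after continued attempts. Nothing bars a person who reappears from the 3-month visit. That part of the reply stands, and the point here does not rely on those readings.

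Nor does a missed visit alone end participation. Contact must also fail after the full search, and a participant who misses a visit but answers the telephone is rescheduled and stays in. That also stands.

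Other parts of the reply limit the size of the problem. GOSE and RPQ are also collected at 2 weeks and 1 month, and the GEE model can use participants with partial data. Exclusion criterion 4 removes people without a reliable telephone number, which makes the upper end of the assumed range less likely. The rates are assumptions throughout. Nothing in the documents shows that loss would differ between arms of a double-blind trial, and the direction of any selection is unknown.

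What the reply does not remove is the sequence itself. Section 7.3 assigns withdrawn status after any visit, section 7.2 attaches replacement to that status, and no text provides for the 3-month attempt, for return, or for the analysis of the person replaced. Partial data in a GEE model do not supply the clinical endpoints, which are defined at 3 months.

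**Conclusion.** The point holds in a limited form. Following sections 7.3 and 7.2 as written can end follow-up before 3 months for a treated participant who has not withdrawn consent, and can put a new participant in the place of a randomised one. The documents do not support the stronger statement that every such participant is permanently removed and no longer sought; they are silent on both.

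The number affected is unknown. About 2 to 8 lost outcomes of 50 follows only from the assumed rates of 10% to 30% unreachable and 30% to 50% recoverable. On similar assumptions the detectable difference changes little: 0.83 to 0.93 SD if nobody is sought, against 0.81 to 0.89 SD if a quarter to a half are reached. The main reasons to act are loss that may be related to outcome and the integrity of the randomised comparison, with precision a lesser one. This is an inexpensive improvement that is worth making. It is not a flaw that invalidates the design.

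**What to change.** In section 7.3:

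- Record a 2-week or 1-month visit at which the participant cannot be reached as a missed visit.
- Repeat the contact attempts already listed at each later visit, including 3 months.
- Say that a participant who reappears may return for the remaining assessments.
- Assign lost to follow-up only after the 3-month visit window has closed, unless consent has been withdrawn. The Schedule of Activities gives no window for that visit, so one has to be stated.

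In section 7.2, state that such participants stay in the randomised analysis set with all available data, even if a replacement is enrolled.

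Section 7.2 also lists a medication interruption of two weeks or longer as a reason for study withdrawal, and someone out of contact may meet it. That listing has to be reconciled with the revised section 7.3 and with section 7.1, which keeps participants who stop medication in follow-up. Otherwise a change to section 7.3 alone may not keep the person in the study. How the passages are reconciled is for the sponsor to decide.

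The cost is a short text change in two sections and a few extra calls by existing coordinators.

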8 STUDY ASSESSMENTS AND PROCEDURES

8.1 EFFICACY ASSESSMENTS

Biomarker Assays: Neurofilament light chain, Intercellular adhesion molecule 5 and brain derived neurotrophic factor will be measured using a single molecule counting technology from Quanterix. Neurogranin will be measured using an ELISA assay made by ADx Neurosciences. high-sensitivity C-reactive protein, IL-6 and IL-10 will be measured using standard ELISA assays.

Other outcome measures: Functional outcome will be assessed with the Glasgow Outcome Scale Extended (GOSE). Symptomatic outcome will be assessed with the Rivermead Post-concussion Symptom Questionnaire (RPQ). Depressive symptoms will be assessed with the Patient Health Questionnaire 9 (PHQ9). These outcomes will be measured at 2 weeks, 1 month, and 3 months. Neurocognitive impairment will be assessed based on a battery of neurocognitive test. These include:

- the Wechsler Test of Adult Reading (WTAR)
- the Hopkins Verbal Learning Test (HVLT) (3 scores),
- the Brief Visuospatial Memory Test - Revised (BVMT-R) (3 scores),
- the Brief Test of Attention (BTA) (1 scores),
- the Trail making test A and B (1 scores),
- the stroop test (2 scores), and
- the Wisconsin Card Sorting Test (WCST) (2 scores),

Using the WTAR (word pronunciation) as an estimate of IQ, we will compare the 13 neurocognitive test T-scores of interest against the subject's IQ T-score. The standard deviation (SD) of T-score is 10. Each of the subject's 13 neurocognitive test T-scores is considered as aberrant if it is more than 2 SD below this subject's IQ T-score. A subject is considered cognitively impaired if at least 2 (based upon .05 rule; 5 out of every 100 test scores will be outside of expected range by chance alone) out the 13 T-scores are aberrant.

8.2 SAFETY AND OTHER ASSESSMENTS

At each study visit, we will evaluate patients for the following:

1. Gastrointestinal distress (nausea, vomiting, diarrhea)
2. Clinically significant bleeding such as intracranial hemorrhage and upper GI bleed

8.3 ADVERSE EVENTS AND SERIOUS ADVERSE EVENTS

8.3.1 DEFINITION OF ADVERSE EVENTS (AE)

Adverse event means any untoward medical occurrence associated with the use of an intervention in humans, whether or not considered intervention-related (21 CFR 312.32 (a)).

8.3.2 DEFINITION OF SERIOUS ADVERSE EVENTS (SAE)

An adverse event (AE) or suspected adverse reaction is considered "serious" if, in the view of either the investigator or sponsor, it results in any of the following outcomes: death, a life-threatening adverse event, inpatient hospitalization or prolongation of existing hospitalization, a persistent or significant incapacity or substantial disruption of the ability to conduct normal life functions, or a congenital anomaly/birth defect. Important medical events that may not result in death, be life-threatening, or require hospitalization may be considered serious when, based upon appropriate medical judgment, they may jeopardize the participant and may require medical or surgical intervention to prevent one of the outcomes listed in this definition. Examples of such medical events include allergic bronchospasm requiring intensive treatment in an emergency room or at home, blood dyscrasias or convulsions that do not result in inpatient hospitalization, or the development of drug dependency or drug abuse.

8.3.3 CLASSIFICATION OF AN ADVERSE EVENT

8.3.3.1 SEVERITY OF EVENT

For adverse events (AEs) not included in the protocol defined grading system, the following guidelines will be used to describe severity.

- **Mild** – Events require minimal or no treatment and do not interfere with the participant's daily activities.
- **Moderate** – Events result in a low level of inconvenience or concern with the therapeutic measures. Moderate events may cause some interference with functioning.
- **Severe** – Events interrupt a participant's usual daily activity and may require systemic drug therapy or other treatment. Severe events are usually potentially life-threatening or incapacitating. Of note, the term "severe" does not necessarily equate to "serious".

8.3.3.2 RELATIONSHIP TO STUDY INTERVENTION

All adverse events (AEs) must have their relationship to study intervention assessed by the clinician who examines and evaluates the participant based on temporal relationship and his/her clinical judgment. The degree of certainty about causality will be graded using the categories below. In a clinical trial, the study product must always be suspect.

- **Definitely Related** – There is clear evidence to suggest a causal relationship, and other possible contributing factors can be ruled out. The clinical event, including an abnormal laboratory test result, occurs in a plausible time relationship to study intervention administration and cannot be explained by concurrent disease or other drugs or chemicals. The response to withdrawal of the study intervention (dechallenge) should be clinically plausible. The event must be pharmacologically or phenomenologically definitive, with use of a satisfactory rechallenge procedure if necessary.
- **Probably Related** – There is evidence to suggest a causal relationship, and the influence of other factors is unlikely. The clinical event, including an abnormal laboratory test result, occurs within a reasonable time after administration of the study intervention, is unlikely to be attributed to concurrent disease or other drugs or chemicals, and follows a clinically reasonable response on withdrawal (dechallenge). Rechallenge information is not required to fulfill this definition.
- **Potentially Related** – There is some evidence to suggest a causal relationship (e.g., the event occurred within a reasonable time after administration of the trial medication). However, other factors may have contributed to the event (e.g., the participant's clinical condition, other concomitant events). Although an AE may rate only as "possibly related" soon after discovery, it can be flagged as requiring more information and later be upgraded to "probably related" or "definitely related", as appropriate.
- **Unlikely to be related** – A clinical event, including an abnormal laboratory test result, whose temporal relationship to study intervention administration makes a causal relationship improbable (e.g., the event did not occur within a reasonable time after administration of the study intervention) and in which other drugs or chemicals or underlying disease provides plausible explanations (e.g., the participant's clinical condition, other concomitant treatments).
- **Not Related** – The AE is completely independent of study intervention administration, and/or evidence exists that the event is definitely related to another etiology. There must be an alternative, definitive etiology documented by the clinician.

8.3.3.3 EXPECTEDNESS

Study research coordinators will be responsible for determining whether an adverse event (AE) is expected or unexpected. An AE will be considered unexpected if the nature, severity, or frequency of the event is not consistent with the risk information previously described for the study intervention.

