2.3 RISK/BENEFIT ASSESSMENT

2.3.1 KNOWN POTENTIAL RISKS

Gastrointestinal distress (nausea, vomiting, diarrhea), low risk of bleeding

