2.3.3 ASSESSMENT OF POTENTIAL RISKS AND BENEFITS

Omega-3 fatty acids have an excellent safety profile. It is FDA approved for treating hypertriglyceridemia. The potential risks from taking omega-3 fatty acids are minimal. Gastrointestinal symptoms resolve upon stopping the medication. The risk of bleeding is minimal and at times disputed. There are currently no treatments for traumatic brain injury. Animal studies have demonstrated that omega-3 fatty acid supplementation may hasten recovery from TBI. Therefore the potential benefits from taking this medication outweigh the risks.

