8.3.4 TIME PERIOD AND FREQUENCY FOR EVENT ASSESSMENT AND FOLLOW-UP

The occurrence of an adverse event (AE) or serious adverse event (SAE) may come to the attention of study personnel during study visits and interviews of a study participant presenting for medical care, or upon review by a study monitor.

All AEs including local and systemic reactions not meeting the criteria for SAEs will be captured on the appropriate case report form (CRF). Information to be collected includes event description, time of onset, clinician's assessment of severity, relationship to study product (assessed only by those with the

training and authority to make a diagnosis), and time of resolution/stabilization of the event. All AEs occurring while on study must be documented appropriately regardless of relationship. All AEs will be followed to adequate resolution.

Any medical condition that is present at the time that the participant is screened will be considered as baseline and not reported as an AE. However, if the study participant's condition deteriorates at any time during the study, it will be recorded as an AE.

Changes in the severity of an AE will be documented to allow an assessment of the duration of the event at each level of severity to be performed. AEs characterized as intermittent require documentation of onset and duration of each episode.

Study research coordinators will record all reportable events with start dates occurring any time after informed consent is obtained until 7 (for non-serious AEs) or 30 days (for SAEs) after the last day of study participation. At each study visit, the investigator will inquire about the occurrence of AE/SAEs since the last visit. Events will be followed for outcome information until resolution or stabilization.

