8.3.5 SERIOUS ADVERSE EVENT REPORTING

The study clinician will immediately report to the sponsor any serious adverse event, whether or not considered study intervention related, including those listed in the protocol or investigator brochure and must include an assessment of whether there is a reasonable possibility that the study intervention caused the event. Study endpoints that are serious adverse events (e.g., all-cause mortality) must be reported in accordance with the protocol unless there is evidence suggesting a causal relationship between the study intervention and the event (e.g., death from anaphylaxis). In that case, the investigator must immediately report the event to the sponsor.

All serious adverse events (SAEs) will be followed until satisfactory resolution or until the site investigator deems the event to be chronic or the participant is stable. Other supporting documentation of the event may be requested by the Data Coordinating Center (DCC)/study sponsor and should be provided as soon as possible.

The study sponsor will be responsible for notifying the Food and Drug Administration (FDA) of any unexpected fatal or life-threatening suspected adverse reaction as soon as possible, but in no case later than 7 calendar days after the sponsor's initial receipt of the information. In addition, the sponsor must notify FDA and all participating investigators in an Investigational New Drug (IND) safety report of potential serious risks, from clinical trials or any other source, as soon as possible, but in no case later than 15 calendar days after the sponsor determines that the information qualifies for reporting.

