8.4 UNANTICIPATED PROBLEMS

8.4.1 DEFINITION OF UNANTICIPATED PROBLEMS (UP)

The Office for Human Research Protections (OHRP) considers unanticipated problems involving risks to participants or others to include, in general, any incident, experience, or outcome that meets all of the following criteria:

- Unexpected in terms of nature, severity, or frequency given (a) the research procedures that are described in the protocol-related documents, such as the Institutional Review Board (IRB)-approved research protocol and informed consent document; and (b) the characteristics of the participant population being studied;
- Related or possibly related to participation in the research (“possibly related” means there is a reasonable possibility that the incident, experience, or outcome may have been caused by the procedures involved in the research); and
- Suggests that the research places participants or others at a greater risk of harm (including physical, psychological, economic, or social harm) than was previously known or recognized.

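### Research coordinators, not a clinician, decide whether an adverse event is expected, and the bleeding-risk text is too thin to guide them, so urgent FDA and IRB reports could be delayed or misdirected

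*Combined protocol and SAP*

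**What the plan says.** Section 8.3.3.3 of the combined protocol and SAP names the decision-maker: "Study research coordinators will be responsible for determining whether an adverse event (AE) is expected or unexpected". It also sets the test: "An AE will be considered unexpected if the nature, severity, or frequency of the event is not consistent with the risk information previously described".

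The neighbouring judgements are assigned differently. Under section 8.3.3.2 all adverse events "must have their relationship to study intervention assessed by the clinician who examines and evaluates the participant". Section 8.3.4 has the case report form carry the clinician's view of severity, and limits the relatedness judgement to people trained and authorised to diagnose.

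Two places describe the bleeding risk of the intervention. Section 2.3.1 reads in full: "Gastrointestinal distress (nausea, vomiting, diarrhea), low risk of bleeding". Section 2.3.3 adds: "The risk of bleeding is minimal and at times disputed".

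Intracranial hemorrhage and upper GI bleed also appear by name in the synopsis, among the SAEs of the fourth secondary objective, and in section 8.2, as events checked at each visit. Neither place says whether they are expected.

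Expectedness then reappears as a reporting condition. Section 8.3.5 has the sponsor notify FDA, within 7 calendar days at most, of "any unexpected fatal or life-threatening suspected adverse reaction as soon as possible". Section 8.4.1 requires all of its three criteria for an unanticipated problem, and the first begins: "Unexpected in terms of nature, severity, or frequency given (a) the research procedures".

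**The concern.** Deciding whether an event fits the known risk profile means judging what the event is and how severe it is. The protocol treats those as clinical questions when it deals with severity and causality. It then hands the one remaining judgement of the same kind to coordinators, and the text available states no clinical review of it.

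The reference they are given is also weak. It says how likely bleeding is, in words, but not where it might occur or how serious it might be. A coordinator who sees bleeding in the risk list, and sees intracranial hemorrhage and upper GI bleed in the list of things to ask about, could in good faith enter a life-threatening bleed as expected.

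At stake is the timing and destination of the most urgent reports. If the label is carried forward without a second look, the FDA 7-day notice and the 24-hour IRB report of a serious unanticipated problem might be late or not made for an event that should have had both.

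**Working it through.** No arithmetic applies: the point uses no rate, error level or sample size. The check sets the sections side by side and follows one event, a life-threatening intracranial bleed, through them.

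**Step 1: who judges what.**
- Severity: the clinician (8.3.4).
- Causality: the examining clinician (8.3.3.2), restricted to those qualified to diagnose (8.3.4).
- Expectedness: research coordinators (8.3.3.3).

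The third judgement uses severity as one of its three limbs, so it draws on a matter that the protocol has already placed with a clinician.

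**Step 2: does the reference text settle the label?**
- Nature: bleeding is listed in 2.3.1, without a site. An intracranial bleed is a form of bleeding, so this limb can be read either way.
- Severity: neither 2.3.1 nor 2.3.3 states one, so there is nothing explicit to compare with.
- Frequency: low (2.3.1) and minimal and disputed (2.3.3) are qualitative, with no figure.

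A mismatch on any one limb makes the event unexpected. A life-threatening intracranial bleed sits poorly with a risk described as low or minimal, so unexpected is the more natural reading. The text does not compel it, and the advance naming in the synopsis and 8.2 pulls the other way for a reader who takes a monitored event to be an expected one.

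**Step 3: what follows if the entry is expected?**

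| Route | Conditional on unexpected? | Who acts | Result |
|---|---|---|---|
| SAE report to sponsor, immediate (8.3.5) | No | Study clinician | Still made, with a causality assessment |
| FDA notice, at most 7 calendar days (8.3.5) | Yes | Sponsor | Not triggered on its wording unless the sponsor judges expectedness itself, which the protocol neither requires nor excludes |
| IND safety report, at most 15 calendar days (8.3.5) | Not as worded; it covers potential serious risks | Sponsor | Remains open |
| IRB unanticipated-problem report, 24 hours if an SAE (8.4.1, 8.4.2) | Yes, one of three required criteria, with its own test | Investigator | Fails if the coordinator's label is carried over; unaffected if the investigator applies the 8.4.1 test afresh |

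Two of the four routes are therefore exposed. In each, a named party could correct the label, but no sentence says whether that party must re-judge it or may rely on it.

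**The case against.** A reader might infer that a life-threatening bleed would drop out of both the FDA and the IRB routes. The documents do not support that. Every SAE goes to the sponsor at once whatever its expectedness, the sponsor owns both FDA reports, and nothing binds the sponsor to the coordinator's entry. The 15-day report is not worded as depending on unexpectedness. The unanticipated-problem definition has its own test, judged against the protocol-related documents and the study population, and the investigator must explain the basis of the report. The event would still be recorded as an adverse event, and clinically significant bleeding is still measured as a secondary endpoint, so the safety signal is not lost.

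It can also be said that low and minimal already point to unexpected, and that the synopsis and 8.2 list events to monitor rather than risk information about the intervention. Both are fair, and I accept the first as the better reading. They reduce the chance of a wrong label but do not exclude it.

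Finally, section 8.3.5 mentions an investigator brochure, section 10.1.1.1 says the consent form describes risks in detail, and the contents list shows a section on key roles and governance (10.1.5). None of these was available here. It cannot be said that a fuller risk list or a medical review of expectedness does not exist. For the same reason, a blanket rule that every serious bleed is unexpected would go further than the documents allow.

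What stands after this is the stated assignment itself: section 8.3.3.3 names coordinators, and two urgent routes use the same concept without saying whose judgement counts.

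**Conclusion.** The point holds as a possible, not an automatic, failure. The protocol gives a partly clinical judgement to coordinators, against risk text that does not settle how a life-threatening bleed should be classed. A wrong label could delay or misdirect two of the four reporting routes, the FDA 7-day notice and the IRB unanticipated-problem report, unless the sponsor or investigator looks again. The other two remain.

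No number of affected events can be given, because the protocol states no bleeding rate.

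The conclusion rests on three assumptions: that the risk information meant in 8.3.3.3 is the text in 2.3; that no unseen document assigns medical review of expectedness; and that the opening sentence of 8.3.5, covering any SAE, governs the immediate report to the sponsor. The change is worth making because it is small and bears directly on safety reporting.

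**What to change.** In section 8.3.3.3:
1. Replace the research coordinators as decision-makers with the blinded investigator or study clinician who already assesses severity and causality. Coordinators can continue to record the events.
2. State that the sponsor's determination of expectedness governs FDA reporting, and the investigator's governs unanticipated-problem reporting under 8.4.
3. Identify the document that serves as the reference risk information, for example section 2.3, the investigator brochure or the consent form.
4. Add a sentence such as: *Listing an event as a monitored safety outcome in the synopsis or section 8.2 does not by itself make it expected.*

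This is a few sentences of text. It needs no new staff, because a clinician already reviews each adverse event for causality. The cost is a small amount of clinician time and possibly slightly more expedited reports.
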